APPENDIX K. CRITERIA FOR POTENTIALLY CLINICALLY SIGNIFICANT EVENTS

Non-DAIDS Criteria for Clinical Laboratory Tests			
Parameter	SI Unit	PCS Low Limit	PCS High Limit
Basophils Percent	%	—	$>4.00 \times \text{ULN}$
Eosinophils Percent	%	—	$>4.0 \times \text{ULN}$
Monocytes percent	%	—	$>4.00 \times \text{ULN}$
Hematocrit	%	$<0.6 \times \text{baseline}$	$>1.3 \times \text{ULN}$
Blood urea nitrogen	mmol/L	—	$>1.3 \times \text{ULN}$
Chloride	mmol/L	$<0.80 \times \text{LLN}$	$>1.1 \times \text{ULN}$
Protein, total	g/L	$<0.8 \times \text{LLN}$	$>1.2 \times \text{ULN}$

LLN=lower limit of normal (value provided by the laboratory); PCS=potentially clinically significant; SI=International System of Units; ULN=upper limit of normal (value provided by the laboratory).

Vital Sign Parameter	Flag	Criterion Value	Change from Baseline
Systolic blood pressure (mmHg)	High (CH)	≥ 180	Increase of ≥ 20 mmHg
	Low (CL)	≤ 90	Decrease of ≥ 20 mmHg
Diastolic blood pressure (mmHg)	High (CH)	≥ 105	Increase of ≥ 15 mmHg
	Low (CL)	≤ 50	Decrease of ≥ 15 mmHg
Heart rate (bpm)	High (CH)	≥ 120	Increase of ≥ 15 bpm
	Low (CL)	≤ 50	Decrease of ≥ 15 bpm
Temperature (°C)	High (CH)	$\geq 38^\circ\text{C}$	Increase of $\geq 1^\circ\text{C}$
	Low (CL)	$<35^\circ\text{C}$	Decrease of $\geq 1^\circ\text{C}$
Respiratory rate (breaths/min)	High (CH)	≥ 30 breaths/min	Increase of ≥ 10 breaths/min
	Low (CL)	≤ 8 breaths/minute	Decrease of ≥ 4 breaths/minute
SpO ₂	Low (CL)	$\leq 93\%$	Decrease of $\geq 3\%$

Note: PCS is meeting either criterion value or change from baseline.

CH=clinically high; CL=clinically low.

- For temperature decreases, the participants baseline value should be accounted for. Scenarios to account for:
 - Participants with fever ($\geq 38^{\circ}\text{C}$ [100.4°F]) at baseline on Day 1 will not be reported as a PCS value unless an increase of $\geq 1^{\circ}\text{C}$ is met post-baseline.
 - Participants with fever ($\geq 38^{\circ}\text{C}$ [100.4°F]) at baseline on Day 1 will not be reported as a PCS value for a decrease in temperature after Day 1 unless to $<35^{\circ}\text{C}$, as this represents clinical improvement in a participant with COVID-19.
- For respiratory rate, the participants baseline value should be accounted for. Scenarios to account for:
 - Participants with a RR >20 breaths/minute at baseline on Day 1 will not be reported as a PCS value for a decrease in RR after Day 1 unless to ≤ 8 breaths/minute, as this represents clinical improvement in a participant with COVID-19.
- For heart rate, the participants baseline value should be accounted for. Scenarios to account for:
 - Participants with a HR >120 bpm at baseline on Day 1 will not be reported as a PCS value for a decrease in HR after Day 1 unless ≤ 50 bpm, as this may represent clinical improvement in a participant with COVID-19.
- Specific values for adolescents may be considered as appropriate.

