5.8.4. Vital Sign Measurements

Vital signs, including temperature, heart rate, respiratory rate, seated blood pressure, and SpO₂ will be summarized using the site staff assessment.

Descriptive statistics for vital signs and for the change from baseline to each post-baseline time point will be presented by treatment group. The number and percentage of participants with a PCS vital sign parameter will be provided for any time post-baseline and separately for the time period of intensive monitoring post-study drug administration. PCS values are provided in [Appendix K](#). Refer to [Appendix B](#) for handling of unscheduled and multiple in-window values.

All vital sign data by participant will also be presented in listings separately for in-person visit and eDiary. Vital Sign listings will include participant recordings and will list data by visit, date and timepoint.

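### Vital signs count as potentially clinically significant on change from baseline alone, which adds a non-specific background to the any-time table, and the heart-rate recovery exemption reaches only 121-124 bpm

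*SAP*

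**What the plan says.** SAP Appendix K gives each vital sign an absolute limit and a change from baseline, and joins them with "Note: PCS is meeting either criterion value or change from baseline". For heart rate, the high flag is 120 bpm or more or a rise of at least 15 bpm, and the low flag is 50 bpm or less or a fall of at least 15 bpm. For respiratory rate, a fall of 4 breaths/min is enough for a low flag. For systolic pressure, 20 mmHg in either direction is enough.

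The appendix then exempts some falls as improvement. Falls from a baseline fever (38 °C or more) are not PCS unless the temperature drops below 35 °C. For respiratory rate, "Participants with a RR >20 breaths/minute at baseline on Day 1 will not be reported as a PCS value for a decrease in RR" unless the rate reaches 8 or less. For heart rate, "Participants with a HR >120 bpm at baseline on Day 1 will not be reported as a PCS value for a decrease in HR" unless it reaches 50 or less. Blood pressure has no exemption.

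SAP Section 5.8.4 states the output: "The number and percentage of participants with a PCS vital sign parameter will be provided for any time post-baseline", with a separate count for the intensive post-dose monitoring period. The same section plans descriptive statistics and change from baseline at each time point by arm, and listings.

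**The concern.** A PCS count should pick out readings worth a clinician's attention. Under the either/or rule, a heart rate going from 95 to 80 bpm, a respiratory rate from 18 to 14, or a systolic pressure from 145 to 125 mmHg is labelled clinically low, although each end value is unremarkable. Such flags arise from ordinary variation and, in people enrolled while ill, from recovery. They accumulate over visits in an any-time table and are mixed there with true breaches of the absolute limits.

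Two things are at stake. A real excess in one arm is harder to see against a high shared background. And if ADG20 speeds recovery, early falls could appear as more low flags in the active arm, which is the reading the exemptions are meant to prevent.

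**Working it through.** **Exemptions against the protocol's own limits (no assumptions).**

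| Sign | Exempt baseline | Excluded at entry (exclusion criterion 2) | Range reached | Sign of moderate disease (protocol Section 2.2.2) |
|---|---|---|---|---|
| Heart rate | above 120 bpm | 125 bpm or more | 121-124 bpm | from 90 bpm |
| Respiratory rate | above 20/min | 30/min or more | 21-29/min | from 20/min |

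The respiratory-rate exemption covers nearly the whole eligible raised range and misses only a baseline of exactly 20. The heart-rate exemption covers four values and misses 90-120 bpm. A fall from 100 to 85 bpm meets the 15 bpm change and is flagged low.

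**Size of the background, heart rate only.** The documents state no expected PCS rate and no within-person SD, so there is no figure of the plan's own to reproduce. The inputs are:
- Limits from Appendix K: 120 and 50 bpm, change of 15 bpm, exemption above 120 bpm.
- Six post-baseline occasions from SAP Section 3.4.4: post-dose, Days 7, 29 and 90, Months 6 and 11. Three of them fall by Day 29.
- Assumed: true baseline mean 85 bpm, between-person SD 10, independent normal reading error with within-person SD s of 4 to 10 bpm, and recovery of 0 or 8 bpm at every post-baseline reading. Baselines of 125 bpm or more are removed.

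For one baseline and one later reading, the difference has SD s√2. Without recovery, the chance that it reaches 15 bpm in either direction is 2Φ(−15/(s√2)). This is 0.8% at s = 4, 7.7% at s = 6, 18.5% at s = 8 and 28.9% at s = 10. With an 8 bpm drop, the chance of a fall of 15 or more is Φ(−7/(s√2)): 10.8%, 20.5%, 26.8% and 31.0%.

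Over several occasions all changes share one baseline reading, so the any-time rate was simulated (400,000 participants per setting):

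| s (bpm) | Either, 6 occasions, no drop | Either, 6 occasions, 8 bpm drop | Criterion value alone, 6 occasions (no drop / drop) | Either, 3 occasions (no drop / drop) |
|---|---|---|---|---|
| 4 | 4% | 35% | 0.4% / 1.7% | 2% / 24% |
| 6 | 31% | 56% | 1.1% / 3.7% | 19% / 41% |
| 8 | 60% | 71% | 2.9% / 6.9% | 41% / 55% |
| 10 | 78% | 83% | 6.2% / 12% | 58% / 66% |

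In this model at most 0.4% of baselines exceed 120 bpm, while 32-36% lie at 90-120 bpm.

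**What the background does to a comparison.** With 399 randomized there are about 200 per arm. Suppose a true effect occurs in 7% of the active arm, independently of the noise flags. On a background p the active-arm rate is p + 0.07(1 − p). Power at two-sided 0.05, from the pooled two-proportion formula, is:
- p = 5%: 5% against 11.65%, power 67%.
- p = 30%: 30% against 34.9%, power 18%.
- p = 60%: 60% against 62.8%, power 8%.

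No test of this table is planned. The figures only show how quickly a difference is diluted.

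**The case against.** The best defence is that PCS means potentially significant, and a sensitive screen is a legitimate choice. It also has support in the text. The primary safety endpoint is change from baseline in vital signs, not the PCS count, and SAP Section 5.8.4 delivers it directly by arm and time point. The post-dose period has its own PCS summary, with a single protocol-required post-injection reading (at 30 minutes), so noise accumulates less there. Noise flags are expected equally in both randomized arms. The fever and respiratory-rate exemptions work. All of this stands, and it is why the point is minor.

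A reader might infer that most participants will be flagged. The documents do not support that: they give no variability. In the model above, without recovery, heart-rate flags stay below half at s = 6 and reach a majority over six occasions at s = 8. A reader might also infer that the table cannot show a signal. It is diluted, not blind, and other outputs carry the same data.

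Nor does it follow that "either" should become "both". Requiring both would drop real breaches of the absolute limits: SpO2 from 94% to 92% (a fall of 2 against the required 3), systolic pressure from 100 to 85 mmHg (15 against 20), or temperature from 37.5 to 38.4 °C (0.9 against 1).

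What the defence does not answer is the mixing of two kinds of flag in one count, and a heart-rate exemption that can hardly ever apply.

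**Conclusion.** The point holds as a matter of presentation and internal consistency. Change alone triggers a PCS label, so the any-time table mixes breaches of the absolute limits with change-only flags. For heart rate the combined background is about 4-78% without recovery and 35-83% with an 8 bpm drop, against 0.4-12% on the criterion value. These ranges rest wholly on the assumed baseline distribution, within-person SDs and recovery drop. The blinded data would narrow them.

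The gap in the heart-rate exemption needs no assumption beyond the entry limit applying to the baseline reading; a baseline of 125 bpm or more would require an eligibility deviation or a rise after eligibility was confirmed. The SAP says a fall from a high heart rate may be improvement, yet the range that the protocol itself lists as a sign of moderate illness is left out. The effect is dilution and some mislabelling of recovery, not loss of the safety evaluation.

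**What to change.** Keep the either/or screen. In the PCS vital-sign table, report by arm and by direction, in separate rows: (a) criterion value met, (b) change from baseline only, and (c) both met. State whether row (a) includes the participants in row (c). No flag is lost, and criterion breaches can be read on their own.

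Reconcile the heart-rate exemption with exclusion criterion 2 and the severity definitions in protocol Section 2.2.2, and record the reason for the limit that is kept. The sponsor's clinical team should choose that limit. Both changes should be made before unblinding.

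The cost is an edited note, some programming and a longer table. No new data are needed.

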3.4.4. Safety Assessments

Safety will be assessed in an ongoing manner. Blood samples for safety laboratory assessments (hematology, serum chemistry, and coagulation) will be collected on Days 1, 7, 29, and 90, and at Month 6. A complete physical examination will be conducted at screening, and a targeted, symptom-directed review of changes in health based on reported AEs or ongoing signs/symptoms of COVID-19 will be conducted at Days 7, 29, and 90, and at Month 6 and Month 11. Vitals signs (including temperature, heart rate, respiratory rate, seated blood pressure, and SpO₂) will be assessed by site staff after study drug dosing and on Days 7, 29, and 90, and at Month 6 and Month 11 (see [Appendix M](#)). Measurements of temperature, SpO₂, and heart rate are to be taken by the participant daily through Day 29.

AEs occurring from when the participant signs the ICF until the Month 14 visit, or withdrawal from the study, will be recorded. Only study procedure-related AEs occurring before randomization will be recorded. Other AEs, including SAEs and MAAEs, will be collected through Month 14. AESIs (as defined in Section [5.8.1.4](#)) will be recorded through Day 4. Participants will record ISRs using the Injection Site Reaction Diary starting after dosing on Day 1 through Day 4. Investigators (or designee) will follow all ISRs that are ongoing beyond Day 4 to resolution. Hypersensitivity reactions and ISRs that occur after Day 4 will be recorded as AEs.

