4. GENERAL STATISTICAL CONSIDERATIONS

4.1. General Rules and Considerations

Continuous variables will be summarized using the following descriptive summary statistics: the number of participants (n), mean, SD, median, first and third quartiles, minimum (min), and maximum (max).

Categorical variables will be summarized using frequency counts and percentages.

Baseline value, unless specified otherwise, is defined as the last non-missing measurement (scheduled or unscheduled) collected on or before the dose of study drug. If the date of dosing is missing, the date of randomization will be used instead.

Unless otherwise specified, the display precision for the summary statistics of all numerical variables will follow programming standards. Please see [Appendix A](#) for variable display standards.

When count data are presented, the percentage will be suppressed when the count is zero in order to draw attention to the non-zero counts. A row denoted “Missing” will be included in count tabulations as needed to account for dropouts and missing values. The denominator for all percentages will be the number of participants in the treatment group within the analysis set of interest, unless otherwise specified.

Change from baseline is defined as the value at the post-baseline visit minus the value at the baseline visit.

Study Day 1 is the calendar day that study drug is administered. Subsequent study days are calculated as the date of assessment/event – date of injection + 1. If a participant is not dosed, the date of randomization is used to define Study Day rather than the date of injection.

Time-to-event variables are defined from the date of dosing. If a participant is not dosed, the date of randomization is used.

All summaries involving diary data will be based on distinct diary date entries.

Unscheduled visits: Unscheduled visit measurements will be included in the analysis as follows:

- In scheduled visit windows per specified visit windowing rules.
- In the derivation of baseline measurements.
- In the derivation of maximum/minimum change from baseline values and worst post-baseline values for safety analyses.
- In individual participant data listings as appropriate.

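### SAP Appendix K lifts the 38 °C criterion for the whole study in participants febrile on Day 1, so a new late fever can go unflagged as potentially clinically significant

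*SAP*

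**What the plan says.** The vital-sign table in SAP Appendix K sets two high-temperature criteria: a value of 38 °C or more, or a rise of 1 °C or more. The table note makes either one sufficient: "Note: PCS is meeting either criterion value or change from baseline".

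The text below the table then carves out participants whose Day 1 temperature was 38 °C or more. A participant with fever "at baseline on Day 1 will not be reported as a PCS value unless an increase of" 1 °C or more is met post-baseline. A companion bullet covers falls: no flag is raised "for a decrease in temperature after Day 1 unless to" below 35 °C, on the ground that a fall is clinical improvement. Both bullets sit under a lead-in about temperature decreases, although the first concerns increases.

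Three other provisions determine how far the carve-out reaches:

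- **Baseline (SAP Section 4.1):** it is "the last non-missing measurement (scheduled or unscheduled) collected on or before the dose of study drug", and change is always measured against that value.
- **Period counted (SAP Section 5.8.4):** "The number and percentage of participants with a PCS vital sign parameter will be provided for any time post-baseline", with a separate count for intensive post-dose monitoring. Protocol Section 7.11 describes the count at each time point assessed.
- **Schedule (SAP Section 3.4.4):** vital signs "will be assessed by site staff after study drug dosing and on Days 7, 29, and 90, and at Month 6 and Month 11".

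**The concern.** The exemption is sensible while the index fever lasts. A participant enrolled at 38.5 °C who still reads 38.3 °C on Day 7 has not developed a new safety finding. But the sentence names no visit, day or return to normal after which the exemption stops, and no other passage supplies one. The same suspension therefore applies at Day 90, Month 6 and Month 11.

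Protocol Sections 1.2 and 1.3.2 expect mild infection to resolve in about 2 to 3 weeks, and Section 1.2 gives 2 to 6 weeks for severe disease. A fever at those late visits is very unlikely to be the index fever. The reason given for the companion bullet, clinical improvement, cannot apply to it.

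Affected participants are to be expected, because a measured temperature of 38 °C or more on the day of randomization is a qualifying sign in inclusion criterion 4. At stake is whether the PCS-high temperature count means the same thing for everyone in its denominator during long-term follow-up.

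**Working it through.** The documents give no PCS figure to reproduce, so the check is on the rule itself.

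**Rule.** Let B be the baseline temperature and T a later site temperature.

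- Table criteria: flag if T ≥ 38.0 °C or T − B ≥ 1.0 °C.
- With the exemption, when B ≥ 38.0 °C: flag only if T − B ≥ 1.0 °C, that is, T ≥ B + 1.0 °C.

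**Lowest flagged value, for assumed baselines.**

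| Baseline B (°C) | Table criteria alone (°C) | Appendix K with exemption (°C) |
|---|---|---|
| 36.8 | 37.8 | 37.8 |
| 38.0 | 38.0 | 39.0 |
| 38.5 | 38.0 | 39.5 |
| 39.0 | 38.0 | 40.0 |
| 39.5 | 38.0 | 40.5 |

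Time does not enter either formula. Evaluating the rule at Days 7, 29, 90, 180 and 330 gives the same answer at each.

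**Example (temperatures assumed).**

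- Participant 1: B = 38.6, normal on Day 7, T = 39.5 at Day 90. Change = 39.5 − 38.6 = +0.9 °C, so no flag.
- Participant 2: B = 37.5, T = 38.0 at Day 90. The change is only +0.5 °C, but T meets the 38 °C criterion, so it is flagged.

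The higher fever is left out and the lower one is counted.

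**Timing.** The Day 90 window is ±14 days, so the first scheduled site temperature after the Day 29 visit is no earlier than Day 90 − 14 = Day 76. Six weeks, the protocol's longest recovery time, is Day 42. Every scheduled temperature after the Day 29 visit thus falls beyond the expected end of the index illness.

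**Comparison with the other exemptions.** The respiratory-rate and heart-rate exemptions in Appendix K also have no end date, but they cover decreases only. Temperature is the one vital sign whose absolute high limit is suspended.

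**Number affected.** This needs the share febrile on Day 1 and the share with a later site-recorded fever; the documents give neither. Purely as an illustration, assume 5% to 20% febrile on Day 1 and 4% to 8% with a late fever, equally likely in both groups. Of 399 randomized, 399 × 0.05 = 20 to 399 × 0.20 = 80 would be exempt. Late fevers among them would number 399 × 0.04 × 0.05 = 0.8 to 399 × 0.08 × 0.20 = 6.4. This is a ceiling under those assumptions: fevers at or above B + 1 °C are still flagged, and the Safety Set contains only dosed participants.

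**The case against.** The strongest reply is that little depends on this flag. The safety endpoints are changes from baseline in vital signs, reported as descriptive statistics by time point, and the exemption does not touch them. PCS status carries no hypothesis test and does not enter the pausing guidelines. The rule is identical in both arms. All of this stands.

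Late fevers also have other routes into the data. All vital signs are listed by participant (SAP Section 5.8.4). Adverse events are collected through Month 14 (protocol Section 6.4.6) and may be identified from any study data (Section 6.4.6.2). The targeted health review at the same visits as the late site temperatures requires clinically significant abnormalities to be documented as adverse events (Section 6.4.4). The exception for worsening of the index COVID-19 does not cover a fever from another cause. This too stands, so the omission is confined to the PCS count.

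A further reply is that the SAP specifies no PCS count restricted to late visits. Section 5.8.4 gives an any-time count, in which early flags dilute any late omission. Only the protocol mentions each time point, and the SAP says it prevails where methods differ. That limits the visible effect, but the any-time count still includes the late visits and still applies two different thresholds there.

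None of these replies supplies an end date or makes the count correct.

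**Conclusion.** The point holds as a minor defect in a written rule. For participants at 38 °C or more on Day 1, the threshold becomes the Day 1 temperature plus 1 °C at every later visit, and the any-time PCS-high temperature count can omit new fevers at Day 90 and Months 6 and 11. The same applies to the by-time-point count if it is produced. The example temperatures are assumed; the rule itself is read directly from Appendix K and SAP Section 4.1.

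The number affected cannot be computed from the documents and is probably small.

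A reader might go further and infer three things that the documents do not support:

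- **That the primary or long-term safety endpoint is understated.** Those endpoints rest on change from baseline, which is summarized without the exemption.
- **That late fevers disappear from the safety data, or that the arms are treated differently.** Adverse-event records and listings remain, and the same rule applies to both arms.
- **That a given percentage of fevers from Day 29 on is missed.** The SAP defines no such count, and any percentage rests on an assumed febrile share.

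**What to change.** In SAP Appendix K, limit the Day 1 fever exemption to assessments through Day 29. After Day 29, apply the 38 °C criterion as for all other participants. The sentence should say whether a Day 29 visit held within its +5-day window falls inside the limit.

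Do not end the exemption at the first reading below 38 °C. Site vital signs are taken 30 minutes after injection (protocol Section 6.4.1) and antipyretics are allowed (Section 5.6.2.3). A single transient or suppressed reading could end the exemption while the index fever continues, and a persisting index fever on Day 7 would then be flagged.

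In the same edit, move the sentence out from under the lead-in on temperature decreases, since it concerns increases.

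The cost is one sentence and a small programming change, with no new data. An index fever that persists beyond Day 29 would be flagged; since no site temperature is scheduled between the Day 29 visit and Day 76, this would arise mainly at unscheduled visits. A new fever up to Day 29 in an exempt participant would still go unflagged unless it exceeds the Day 1 value by 1 °C. That is acceptable, because temperature alone cannot separate it from the index illness.
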